8.2.4. Spirometry Test

Participant's baseline pulmonary disease must have a spirometry test during the Screening Phase and then repeat evaluation per the Schedule of Activities Table 1/Table 1A.

8.2.5. ECOG Performance Status

The ECOG Performance Status scale will be used to grade changes in the participant's daily living activities. The ECOG Performance Status scale is provided in Appendix 6 Section 10.6. The frequency of ECOG Performance Status assessment is provided in the Schedule of Activities Table 1/Table 1A.

8.2.6. Clinical Safety Laboratory Assessments

Blood samples for serum chemistry and hematology will be collected as noted in Appendix 2 Section 10.2, Clinical Laboratory Tests. The investigator must review the laboratory results, document this review, and record any clinically relevant changes occurring during the study in the adverse event section of the eCRF. The laboratory reports must be filed with the source documents.

The following laboratory elevations may indicate severe liver injury (possible Hy's law) and further workup and testing should be strongly considered. See Section 6.6 for study treatment dose modification guidelines.

- For participants with normal baseline AST, ALT and bilirubin, all events of AST or ALT $\geq 3 \times$ upper limit of normal (ULN) and bilirubin $\geq 2 \times$ ULN
- For participants with baseline ALT or AST $\geq 3 \times$ ULN, all events with ALT or AST ≥ 3 times baseline values in the absence of concurrent bilirubin elevations or new symptoms
- For participants with baseline ALT or AST $\geq 3 \times$ ULN, all events with ALT or AST $\geq 2 \times$ baseline values if concurrent bilirubin elevations or symptoms occur or no alternative causes are found.
- For participants with baseline bilirubin $\geq 2 \times$ ULN, all events with bilirubin $\geq 2x$ baseline

8.3. Adverse Events and Serious Adverse Events

Timely, accurate, and complete reporting and analysis of safety information from clinical studies are crucial for the protection of participants, investigators, and the Sponsor, and are mandated by regulatory agencies worldwide. The Sponsor has established Standard Operating Procedures in conformity with regulatory requirements worldwide to ensure appropriate reporting of safety information; all clinical studies conducted by the Sponsor or its affiliates will be conducted in accordance with those procedures. Adverse events will be reported by the participant (or, when appropriate, by a caregiver, surrogate, or the participant's legally acceptable representative).

For further details on adverse events and serious adverse events (Definitions and Classifications; Attribution Definitions; Severity Criteria; Special Reporting Situations; Procedures) as well as product quality complaints, refer to Appendix 4 Section 10.4, Adverse Events: Definitions and Procedures for Recording, Evaluating, Follow-Up, and Reporting.

8.3.1. Time Period and Frequency for Collecting Adverse Event and Serious Adverse Event Information

All Adverse Events

All adverse events and special reporting situations, whether serious or non-serious, will be reported from the time a signed and dated ICF is obtained until 30 days after the last dose of study intervention or until the start of subsequent anti-AML therapy, if earlier. Serious adverse events, including those spontaneously reported to the investigator within 30 days after the last dose of study intervention, must be reported using the Serious Adverse Event Form. The Sponsor will evaluate any safety information that is spontaneously reported by an investigator beyond the time frame specified in the protocol.

Serious Adverse Events

All serious adverse events occurring during the study must be reported to the appropriate Sponsor contact person by study-site personnel within 24 hours of their knowledge of the event.

Information regarding serious adverse events will be transmitted to the Sponsor using the Serious Adverse Event Form, which must be completed and signed by a physician from the study site and transmitted to the Sponsor within 24 hours. The initial and follow-up reports of a serious adverse event should be made by facsimile (fax).

8.3.2. Method of Detecting Adverse Events and Serious Adverse Events

Care will be taken not to introduce bias when detecting adverse events or serious adverse events. Open-ended and nonleading verbal questioning of the participant is the preferred method to inquire about adverse event occurrence.

Solicited Adverse Events

Solicited adverse events are predefined local at the injection site and systemic events for which the participant is specifically questioned.

Unsolicited Adverse Events

Unsolicited adverse events are all adverse events for which the participant is not specifically questioned. Care will be taken not to introduce bias when detecting adverse events or serious adverse events. Open-ended and nonleading verbal questioning of the participant is the preferred method to inquire about adverse event occurrence.

8.3.3. Follow-up of Adverse Events and Serious Adverse Events

Adverse events, including pregnancy, will be followed by the investigator as specified in Appendix 10.4, Adverse Events: Definitions and Procedures for Recording, Evaluating, Follow-up, and Reporting.

8.3.4. Regulatory Reporting Requirements for Serious Adverse Events

The Sponsor assumes responsibility for appropriate reporting of adverse events to the regulatory authorities. The Sponsor will also report to the investigator (and the head of the investigational institute where required) all suspected unexpected serious adverse reactions (SUSARs). The investigator (or Sponsor where required) must report SUSARs to the appropriate Independent Ethics Committee/ Institutional Review Board (IEC/IRB) that approved the protocol unless otherwise required and documented by the IEC/IRB.

8.3.5. Adverse Events of Special Interest

Grade ≥ 3 IRR will be followed as part of standard safety monitoring activities by the Sponsor. These events will be reported to the Sponsor within 24 hours of awareness irrespective of seriousness (ie, serious and nonserious adverse events) following the procedure described above for serious adverse events and will require enhanced data collection.

8.3.6. Pregnancy

All initial reports of pregnancy in female participants or partners of male participants must be reported to the Sponsor by the study-site personnel within 24 hours of their knowledge of the event using the appropriate pregnancy notification form. Abnormal pregnancy outcomes (eg, spontaneous abortion, fetal death, stillbirth, congenital anomalies, ectopic pregnancy) are considered serious adverse events and must be reported using the Serious Adverse Event Form. Any participant who becomes pregnant during the study must withhold treatment of the study intervention and notify the Sponsor's clinical team. Follow-up information regarding the outcome of the pregnancy and any postnatal sequelae in the infant will be required.

8.4. Treatment of Overdose

For this study, any dose of cusatuzumab greater than 20 mg/kg, within a 24-hour time period will be considered an overdose.

In the event of an overdose, the investigator or treating physician should:

- Contact the Sponsor immediately. The Sponsor's clinical team will evaluate the extent of an overdose and will determine if the measures outlined below should be followed.

- Closely monitor the participant for AE/SAE and laboratory abnormalities for a minimum of 90 days.
- Obtain a serum sample for PK analysis within 3 days from the date of the last dose of study intervention if requested by the Medical Monitor (determined on a case-by-case basis).
- Document the quantity of the excess dose as well as the duration of the overdosing in the eCRF.

Decisions regarding dose interruptions or modifications will be made by the investigator in consultation with the Medical Monitor based on the clinical evaluation of the participant.

8.5. Pharmacokinetics

Serum samples will be used to evaluate the PK of cusatuzumab. In addition, limited bone marrow aspirates may be used to evaluate cusatuzumab concentration in bone marrow. Limited plasma samples will be used to evaluate PK of azacitidine. Serum collected for PK may additionally be used to evaluate safety or efficacy aspects that address concerns arising during or after the study period. Genetic analyses will not be performed on these serum samples. Participant confidentiality will be maintained.

8.5.1. Evaluations

Venous blood samples of approximately 7 mL will be collected for measurement of serum concentrations of cusatuzumab and anti-cusatuzumab antibodies as suggested in the Schedule of Activities (Table 1/Table 1A). In addition to serum samples, plasma samples will be analyzed for measurement of azacitidine concentrations.

Venous blood samples will be collected and each serum sample will be divided into 4 aliquots. Samples collected for analyses of cusatuzumab serum concentration and antibodies to cusatuzumab may additionally be used to evaluate safety or efficacy aspects that address concerns arising during or after the study period, for further characterization of immunogenicity or for the evaluation of relevant biomarkers. Genetic analyses will not be performed on these serum samples. Participant confidentiality will be maintained. Additional information about the collection, handling, and shipment of biological samples can be found in the Laboratory Manual.

8.5.2. Analytical Procedures

Pharmacokinetics

Plasma and serum samples will be analyzed to determine concentrations of azacitidine and cusatuzumab, respectively, using validated, specific, and sensitive (eg, immunoassay and LC-MS/MS) methods by or under the supervision of the Sponsor. Additionally, concentrations of cusatuzumab in bone marrow will be determined for a small number of participants.

Immunogenicity

The detection and characterization of anti-cusatuzumab antibodies will be performed using a validated assay method by or under the supervision of the Sponsor. All samples collected for

detection of anti-cusatuzumab antibodies will also be evaluated for cusatuzumab serum concentration to enable interpretation of the antibody data.

Anti-cusatuzumab antibodies will be evaluated in serum samples collected from all participants according to the Schedule of Activities. Additionally, serum samples should also be collected at the final visit from participants who are discontinued from intervention or withdrawn from the study. These samples will be tested by the Sponsor or Sponsor's designee.

Serum samples will be screened for antibodies binding to cusatuzumab and the titer of confirmed positive samples will be reported. Other analyses may be performed to further characterize the immunogenicity of cusatuzumab.

Serum samples will be used to evaluate the immunogenicity of anti-cusatuzumab antibodies. Samples collected for immunogenicity analyses may additionally be used to evaluate safety or efficacy aspects that address concerns arising during or after the study period. Genetic analyses will not be performed on these serum samples. Participant confidentiality will be maintained.

Receptor Occupancy

Whole blood samples will be analyzed for RO via flow cytometry.

8.5.3. Pharmacokinetic Parameters and Evaluations

Parameters

Based on the individual serum concentration-time data, using the actual dose taken and the actual sampling times, PK parameters and exposure information of cusatuzumab will be derived using population PK modelling. Baseline covariates (eg, body weight, age, sex, CrCL, race) may be included in the model, if relevant.

Pharmacokinetic/Pharmacodynamic Evaluations

If sufficient data are available, pharmacokinetic/pharmacodynamic modeling may be performed, including exploring the relationship between serum concentrations of cusatuzumab and biomarkers, PD markers, or endpoints of clinical efficacy. If these analyses are performed, the details and results will be presented in a separate report.

8.6. Genetics

Genetics are not evaluated in this study, however, somatic mutations are evaluated in the tumor cells as described in Section 8.8.

8.6.1. Cytogenetics/ Mutational Analysis

Assessment of mutational status must be performed per schedule of activities (Table 1/Table 1A) and must include testing for all mutations listed in Appendix 10. Central and/or local testing is acceptable. Bone marrow collected at screening is preferred for mutational analyses. However, standard-of-care assessment of mutational status obtained prior to the ICF signing will be accepted in lieu of screening marrow, provided that it includes testing for all mutations listed in Appendix

10. Left over fresh or frozen bone marrow samples may be requested for central mutational analysis if all tests are not performed by the local study site.

8.7. Pharmacodynamics

Samples of bone marrow aspirates or whole blood for pharmacodynamics evaluations will be collected as specified in the Schedule of Activities Table 2. Biomarker tests will include, but not limited to: evaluation of CD70 and CD27 expression level and decrease numbers of blasts and leukemia stem cells (LSC) in whole blood and bone marrow by flow cytometry, mRNA levels for CD70, CD27 and other CD70-CD27 signaling-related genes, and LSC gene signature by transcriptome analysis. Serum samples will be collected and used for protein quantification for evaluation of soluble CD27 and may be for inflammatory cytokines. The changes in pharmacodynamic parameters from baseline to timepoints specified in the Schedule of Activities (Table 2) will be analyzed.

8.8. Biomarkers

Samples for biomarker evaluations will be collected as specified in The Schedule of Activities Table 2. The baseline levels and changes from baseline in biomarkers will be analyzed. Additional information about the collection, handling, and shipment of biological samples can be found in the Laboratory Manual.

The biomarkers to be tested in this study are based on the cusatuzumab mechanism of action, treatment with cusatuzumab results in induction of cytotoxicity against CD70-positive tumor cells by antibody effector mechanisms (enhanced ADCC, ADCP, CDC), by blocking proliferation and survival signals of malignant cells, and by induction of an anti-tumor immune response following interruption of CD70-CD27 signaling. The approaches of biomarker tests include, but not limited to, the following:

Flow cytometry/ CyTOF: The main mechanism of action of cusatuzumab is ADCC through NK cell activation, therefore, bone marrow aspirates or whole blood will be analyzed for immunophenotyping by flow cytometry for NK cell counts and biomarker of NK cell activation. In addition, B cells, T cell subsets, and other immune cell subpopulations, such as activated T cells, Treg, may be evaluated by flow cytometry and/or CyTOF. An additional mechanism of action may be through the induction of myeloid differentiation. Bone marrow aspirates will be evaluated for markers of differentiation by flow cytometry. These assessments will be evaluated for the association with clinical outcome.

Genomic analysis: DNA sequencing from tumor cells will be performed to identify mutations for characterization of disease subtype and potential predictive biomarkers of response and resistance. DNA methylation analysis may be performed.

Gene expression/transcriptome profile: RT-PCR or RNAseq analysis for evaluating the effect of cusatuzumab plus azacitidine on mRNA levels of CD70, CD27, genes involved in CD70/CD27 signaling pathways, and leukemic stem cell (LSC) signature. Baseline transcriptome profile will be correlated to clinical response to identify gene signatures potential predict response to

cusatuzumab plus azacitidine.

Minimal/measurable residual disease (MRD) assessment: MRD assessments will be performed on bone marrow aspirates and whole blood samples collected from all participants at baseline by flow cytometry and molecular methods such as next generation of sequence (NGS) or droplet PCR to establish the clone for MRD monitoring. Additional bone marrow aspirate and whole blood sample will be taken for participants at suspected CR, then follow up until relapse or EOT to assess duration of MRD negativity. For flow cytometry MRD assay, the cutoff for MRD negativity is defined as less than 1 blast in 1,000 leukocytes (MRD level $<10^{-3}$ as recommended by the ELN.⁶ In addition, other lower cutoff values will be evaluated for MRD negativity.

Additional Collections

Additional blood samples will be collected if a participant experiences Grade 3 or greater infusion-related reactions for cytokine analysis. If it is determined at any time before study completion that additional material is needed for the successful completion of the protocol-specified analyses, the Sponsor may request that additional material be retrieved from existing samples. Also, based on emerging scientific evidence, the Sponsor may request additional material from previously collected tumor samples during or after study completion for a retrospective analysis. In this case, such analyses would be specific to research related to the study intervention(s) or diseases being investigated.

Stopping Analysis

Biomarker analyses are dependent upon the availability of appropriate biomarker assays and clinical response rates. Biomarker analysis may be deferred or not performed, if during or at the end of the study, it becomes clear that the analysis will not have sufficient scientific value for biomarker evaluation, or if there are not enough samples or responders to allow for adequate biomarker evaluation. In the event the study is terminated early or shows poor clinical efficacy, completion of biomarker assessments is based on justification and intended utility of the data.

8.9. Patient-Reported Outcomes

Patient-reported outcome assessments will be conducted as described in the Schedule of Activities (Table 1/Table 1A). Patient-reported outcome assessments should be completed at the beginning of the corresponding assessment, before any other assessments, examinations, or treatments following the PRO completion guidelines.

Patient-reported outcome instruments will be administered on paper forms to be filled out directly by the participant, except in the cases of follow-up assessments that may be conducted by telephone or under special circumstances as described in the PRO completion guidelines (eg, assisted administration for participants with visual impairment). In the event that PRO assessments cannot be completed as scheduled during a site visit it should be entered in the eCRF.

Patient-reported outcome instruments included in this study are the Functional Assessment of Cancer Therapy – Leukemia (FACT-Leu) and EuroQoL 5 Dimension 5 Level questionnaire (EQ-5D-5L).

The FACT-Leu is a 44-item instrument measuring health-related quality of life concepts. It is comprised of 4 subscales that make up the FACT-G: physical well-being (PWB, 7 items), social/family well-being (SWB, 7 items), emotional well-being (EWB, 6 items), and functional well-being (FWB, 7 items) and a fifth subscale for leukemia-specific concerns (LeuS, 17 items). Items are rated on a response scale from 0 (not at all) to 4 (very much). Subscale and total scores may be calculated according to instrument administration and scoring guidelines; higher scores indicated better health-related quality of life.

The EQ-5D consists of 5 items describing health state and the EuroQoL visual analog scale (VAS) of self-rated overall health. Responses for the 5 descriptive items are converted into a single index value or utility score according to EQ-5D scoring algorithm ranging from -1 to 1 where lower scores indicate worse health status. EQ-5D-VAS responses range from 0 (the worst health you can imagine) to 100 (the best health you can imagine).

Minimum important difference (MID) thresholds for improvement/worsening will be specified in the statistical analysis plan for any PRO score analyses requiring a threshold. All PRO scale scores will be calculated according to published instrument manuals (ie, administration and scoring guidelines) for scoring and handling of missing data unless otherwise specified.

8.10. Medical Resource Utilization

Medical resource utilization data, associated with medical encounters, will be collected in the eCRF by the investigator and study-site personnel for all participants throughout the study. Protocol-mandated procedures, tests, and encounters are excluded. The data collected may be used to conduct exploratory economic analyses and will include:

- Number and duration and reasons for medical care encounters, including surgeries, and other selected procedures (inpatient and outpatient)
- Duration of hospitalization (total days length of stay, including duration by wards; eg, intensive care unit)
- Number and character of diagnostic and therapeutic tests and procedures
- Outpatient medical encounters and treatments (including physician or emergency room visits, tests and procedures, and medications) and reasons

9. STATISTICAL CONSIDERATIONS

Detailed statistical methods used in the study design are described in this section. Statistical analysis will be done by the Sponsor or under the authority of the Sponsor. A general description of the statistical methods to be used to analyze the efficacy and safety data is outlined below. Specific details will be provided in the Statistical Analysis Plan.

9.1. Statistical Hypotheses

The primary hypothesis is that participants treated with the combination of cusatuzumab (at a dose level of 10 mg/kg or 20 mg/kg) and azacitidine can achieve a CR rate of 35% or greater against the null hypothesis of 20%.

9.2. Sample Size Determination

Up to 50 participants will be enrolled for each dose group in Part 1 of the study. Part 1 will utilize a 3-stage monitoring approach to determine, at each stage and for each dose group, if the observed CR rate warrants the respective dose to be continued into the next stage or into Part 2 of the study (see details in Section 9.5, Interim Analysis). Participants will be enrolled into Part 2 at the selected cusatuzumab dose until a cumulative total of 100 participants have been treated with the selected dose from Part 1 and Part 2. The study has a >90% power to reject the null hypothesis of a CR rate of 20% under the alternative hypothesis of 35% for a total of 100 participants (from Part 1 and Part 2) at the selected dose level. This sample size is based on the single-arm Wilson Score test without continuity correction at an overall 1-sided type 1 error rate <2.5%.

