The safety of cusatuzumab will be assessed by physical examinations, Eastern Cooperative Oncology Group (ECOG) performance status, clinical laboratory tests, vital signs, and adverse event monitoring.

STATISTICAL METHODS

[figure not shown]
Part 1 of the study will utilize a 3-stage monitoring approach to determine, at each stage and for each dose group, if the observed CR rate warrants the respective dose to be continued into the next stage or into Part 2 of the study. Only 1 dose will be selected to continue to Part 2. Participants will be enrolled into Part 2 at the selected cusatuzumab dose until a cumulative total of 100 participants have been treated with the selected dose from Part 1 and Part 2. The study has a >90% power to reject the null hypothesis of a CR rate of 20% under the alternative hypothesis of 35% for a total of 100 participants (from Part 1 and Part 2) at the selected dose level. This sample size is based on the single-arm Wilson Score test without continuity correction at an overall 1-sided type 1 error rate <2.5%.

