9.4. Statistical Analyses

9.4.1. Efficacy Analyses

Binary endpoints will be summarized with number and percentage of participants achieving the endpoint along with the corresponding 2-sided 95% exact confidence interval. These endpoints include CR, CR + CRh, CR+CRh+CRi, CR without MRD, MRD negativity, and transfusion independence. Hypothesis testing for the primary endpoint of CR rate will be performed using the Wilson Score test without continuity correction against the null hypothesis of 20% at the planned interim and final analyses (see Section 9.5, Interim Analysis).

The Kaplan-Meier method will be used to summarize time-to-events endpoints, including time to CR, time to CR + CRh + CRi, duration of CR, duration of CR+ CRh + CRi, PFS, and OS. Time to and duration of response are defined only for participants who achieved such responses; PFS and OS are defined for all participants. Duration of transfusion independence will also be summarized for participants who achieved such status.

No formal hypothesis testing or formal statistical comparison between the 2 dose groups is planned for study Part 1.

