9.5. Interim Analyses

For each analysis (3 stages in Part 1 and the formal interim and final analysis in Part 2), the data cutoff will be the time point when the last participant in the respective analysis has been treated for a minimum of 3 cycles (Part 1) or 4 cycles (Part 2) of the combination therapy.

NOTE: Part 2 of the study will not be conducted because further development of this regimen (cusatuzumab in combination with azacitidine) in patients with unfit AML will not be pursued due to the evolving treatment landscape in AML.

Study Part 1

Part 1 of the study consists of 3 stages of monitoring to select a dose schedule. The cumulative number of participants for each dose group at each of the 3 stages are 15, 30, and 50, respectively. At each stage, each dose group's response rate will determine independently (without formal statistical comparison to the other group) if that dose group will be stopped or continued into the next stage or into study Part 2. Only 1 dose group will be selected for Part 2. The statistical criteria for such a determination will be based on the number (and percentage) of participants in each dose group achieving CR.

The purpose of the 3-stage monitoring in Part 1 is to select, or to eliminate a dose, which will be based on the Pocock beta-spending function with an overall beta level of 10% allocated to the 3 stages with respective and cumulative sample sizes of 15 (30%), 30 (60%), and 50 (100%) participants per group. Per this approach, the statistical decision criteria and corresponding inferences are summarized in Table 7, where 2 possible outcomes resulting in a stop or continuation decision, respectively, are presented for each stage.

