1.6. Changes of Study Conduct and Planned Analyses

The study did not proceed into Part 2 per decision by study Sponsor and the DRC upon completion of the analyses in all 3 stages in study Part 1. Data from study Part 1 will be summarized with descriptive statistics without formal comparison or hypothesis testing.

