4. EFFICACY

4.1. Primary Efficacy Endpoint, CR Rate

Number and percent of participants achieving CR will be provided by treatment arm and the 2 arms combined along with 95% CI. Analyses will be performed for ITT and MITT populations.

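### Does the >90% power statement mislead now that Part 2 is cancelled and only up to 50 participants per arm remain?

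*Protocol*

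**What the plan says.** The statistical paragraph of the synopsis states: "The study has a >90% power to reject the null hypothesis of a CR rate of 20% under the alternative hypothesis of 35" per cent. Protocol 9.2 repeats this and ties it to its condition, "under the alternative hypothesis of 35% for a total of 100 participants (from Part 1 and Part 2) at the selected dose level". SAP 1.4 makes the same claim after describing enrolment to a cumulative 100 at the selected dose. The test is the one-sided Wilson score test without continuity correction, with overall type I error below 2.5%. Protocol 9.1 and SAP 1.3 keep the matching hypothesis, that participants "can achieve a CR rate of 35% or greater against the null hypothesis of 20" per cent.

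Other current text withdraws the second half of that design. Protocol 9.5 says: "NOTE: Part 2 of the study will not be conducted because further development of this regimen". The same note stands in the synopsis (overall design), the schema, 2.1.1 and 4.1. SAP 1.6, the section on changes to conduct and planned analyses, says the study did not go on to Part 2 and adds: "Data from study Part 1 will be summarized with descriptive statistics without formal comparison or hypothesis testing".

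Protocol 9.4.1 says that testing of the CR rate "will be performed using the Wilson Score test without continuity correction against the null hypothesis of 20" per cent, and places that test at the planned interim and final analyses, which 9.5 defines only for Part 2. It closes by planning no formal testing or comparison between the doses in Part 1. For binary endpoints it asks for a percentage "along with the corresponding 2-sided 95% exact confidence interval". SAP 4.1 says: "Number and percent of participants achieving CR will be provided by treatment arm and the 2 arms combined along with 95% CI", without naming the type of interval.

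**The concern.** The places where a reader looks for the sample size rationale describe enrolment into a part that was dropped, and give a power that no arm can have. Someone who read only those places would expect an interval of about 10 points either side of a CR rate near 35%; with 50 per arm it is about 14. They might also expect a test against 20% that will not be done.

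The unnamed interval in SAP 4.1 adds to this. Protocol section 9 leaves specific details to the SAP, and the only method the SAP names for a CR proportion is Wilson. An analyst working from the SAP alone might use Wilson where the protocol asks for exact. At 16 responders in 50, that choice decides whether 20% lies inside the interval.

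**Working it through.** **Inputs.** Null rate 20% and alternative 35% (protocol 9.1). Looks at 80 and 100 participants, with one-sided nominal levels 0.01221 and 0.02144 (protocol 9.5). Wilson score test without continuity correction, overall one-sided error below 2.5% (protocol 9.2). Up to 50 per dose group in Part 1 (protocol 9.2); 50 is assumed below.

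**1. The plan's own figure.** The score statistic is z = (x/n − 0.20)/√(0.16/n).

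| Responders | z | One-sided p | Level | Reject? |
|---|---|---|---|---|
| 24/80 | 2.236 | 0.0127 | 0.01221 | no |
| 25/80 | 2.516 | 0.0059 | 0.01221 | yes |
| 28/100 | 2.000 | 0.0228 | 0.02144 | no |
| 29/100 | 2.250 | 0.0122 | 0.02144 | yes |

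The rule is therefore at least 25/80, or failing that at least 29/100. Exact binomial recursion over the two looks gives:

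- power at a true rate of 35%: 0.9197;
- type I error at 20%: 0.0231.

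Both stated properties hold: power above 90% and error below 2.5%. This calculation leaves out the Part 1 stopping criteria, which 9.5 calls guidance. If they were treated as binding, the power would be about 83%.

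**2. The same test on one arm of 50.** 15/50 gives z = 1.768 and p = 0.0385; 16/50 gives z = 2.121 and p = 0.0169. At one-sided 2.5% the rule would be at least 16/50.

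- Power at 35%: P(X ≥ 16) = 0.720.
- Type I error at 20%: P(X ≥ 16) = 0.031, above the 2.5% limit.
- With at least 17/50, the lowest count at which the exact interval excludes 20%: power 0.611, type I error 0.014.

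These are illustrations only, because SAP 1.6 plans no such test.

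**3. Precision of what will be reported.** Exact 95% intervals:

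| Responders | Interval | Half-width |
|---|---|---|
| 18/50 | 22.9% to 50.8% | (50.8 − 22.9)/2 = 14.0 points |
| 36/100 | 26.6% to 46.2% | (46.2 − 26.6)/2 = 9.8 points |

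SAP 4.1 also reports the two arms combined. With two full arms that is 50 + 50 = 100 participants, so an interval of about 10 points either side does apply to one reported estimate, though not to either dose alone.

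**4. Exact or Wilson.** At 16/50 the exact interval is 19.5% to 46.7% and the Wilson interval 20.8% to 45.8%. Over counts from 1 to 29 out of 50, this is the only one at which the two disagree about 20%. It has probability 0.109 per arm if the true rate is 35%.

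**5. Which text governs.** Protocol 9.2 refers the reader to 9.5, which gives the cancellation note before it describes any analysis. SAP 1.6 follows SAP 1.3 to 1.5 and states what changed. The Wilson test in 9.4.1 belongs to analyses that no longer take place. Read together, these passages lead to one analysis: CR by arm and combined, with an interval and no test.

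**The case for a change.** The strongest case for a change is that the cancellation note was added in many places but not where the sample size is justified. SAP 1.4 still enrols into Part 2 in the future tense, two sections before SAP 1.6 says Part 2 did not happen. The closing sentence of 9.4.1 can be read as ruling out only comparisons between doses, so SAP 1.6 alone clearly excludes a one-sample test. No sample size section gives the precision of 50 per arm, and SAP 4.1 leaves the interval unnamed. The repair would be wording only.

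The description of the text is accurate, and a one-line note in the three places would be tidier. The following limits its weight:

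- The power sentence in the synopsis and in 9.2 carries its own condition of 100 participants from both parts, and is correct under it.
- The size of 50 has a stated basis in the three-stage monitoring of 9.5. Table 7 gives the decision rules and error rates at n = 50, and Table 8 the operating characteristics (98.4%, 74.3% and 72.1%).
- SAP 4.1 is silent on the interval and does not contradict the protocol, which says exact. An analyst with both documents has the answer.
- Adding the 72% and 61% figures would do harm. They are powers for a test that will not be run, the 72% rule has 3.1% error against the plan's limit of 2.5%, and they would bring back 20% as a benchmark in a descriptive analysis.

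**Conclusion.** No change follows. The >90% figure is arithmetically right (92.0% power, 2.3% type I error) for the two-part design to which it is tied, and it now serves as a record of how the study was planned. Protocol 9.5 and SAP 1.6 settle what is done instead, and an analyst who follows them reports the CR rate with an interval and no test.

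The loss from 100 to 50 per arm is real, about 14 points against about 10 on the half-width near 35%. It comes from dropping Part 2 rather than from the wording, and every reported interval will show it. The gap over the interval type is filled by protocol 9.4.1. It would alter the reading against 20% at one count only, 16/50, and no decision rests on that.

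This rests on three assumptions: arms of 50, analysts reading the SAP together with the protocol, and SAP 1.6 prevailing over SAP 1.3 to 1.5. What remains is clerical: a cross-reference missing in three places and one word not repeated.
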